2.1 Primary Objectives

1. To demonstrate the vaccine seroresponse sufficiency of meningococcal serogroups A, C, Y, and W following the administration of a booster dose of MenACYW conjugate vaccine in Group 1 subjects who were first vaccinated with 1 dose of MenACYW conjugate vaccine 3-6 years before the booster dose
2. To demonstrate the vaccine seroresponse sufficiency of meningococcal serogroups A, C, Y, and W following the administration of a booster dose of MenACYW conjugate vaccine in Group 2 subjects who were first vaccinated with 1 dose of Menveo vaccine 3-6 years before the booster dose

The endpoints for the primary objectives are presented in [Section 9.1.1.1](#).

2.2 Secondary Objectives

3. To describe the vaccine seroresponse, seroprotection (hSBA titer $\geq 1:8$), and antibody responses (geometric mean titers [GMTs]) of meningococcal serogroups A, C, Y, and W measured using hSBA in serum specimens collected 6 days (± 1 day) after vaccination in a subset of 50 subjects per group (Groups 1 and 2)
4. To describe the vaccine seroresponse, seroprotection (hSBA titer $\geq 1:8$), and antibody responses (GMTs) to serogroups A, C, Y, and W measured using hSBA on D0 (pre-vaccination) and D30 (+14 days) after vaccination with MenACYW conjugate vaccine alone (Groups 1 and 2)

5. To describe the antibody persistence (GMTs and vaccine seroprotection; hSBA titer $\geq 1:8$) of meningococcal serogroups A, C, Y, and W before a booster dose in subjects who received either MenACYW conjugate vaccine or Menveo vaccine 3-6 years earlier
6. To describe the antibody persistence (GMTs and vaccine seroprotection; hSBA titer $\geq 1:8$) of meningococcal serogroups A, C, Y, and W in subjects who received either a single dose MenACYW conjugate vaccine (subjects randomized to MET59 Groups 1, 3, and 4) or Menveo vaccine (subjects assigned to MET59 Group 2), as part of study MET50, or MET43 (subjects randomized to MET59 Groups 1, 3 and 4)
7. To describe the vaccine seroresponse, seroprotection (hSBA titer $\geq 1:8$), and antibody responses (GMTs) to the antigens present in MenACYW conjugate vaccine, when MenACYW conjugate vaccine is given concomitantly with MenB vaccine (Groups 3 and 4), compared to those when it is given alone (Group 1)

The endpoints for the secondary objectives are presented in [Section 9.2.1.1](#).

2.3 Observational Objectives

Immunogenicity

1. To describe the kinetics of antibody titers against meningococcal serogroups (A, C, Y, and W) measured by hSBA assessed at D0, D06 (only for Groups 1 and 2), D30 after vaccination with MenACYW conjugate vaccine when it is administered alone or concomitantly with MenB vaccines, and also at baseline and D30 in subjects after having received a single dose of either MenACYW conjugate vaccine (subjects randomized to MET59 Groups 1, 3, and 4) or Menveo vaccine (subjects assigned to MET59 Group 2), as part of study MET50, or MET43 (subjects randomized to MET59 Groups 1, 3 and 4)
2. To describe the antibody responses to the meningococcal serogroups A, C, Y, and W before and 30 days (+14 days) after vaccination with MenACYW conjugate vaccine measured by serum bactericidal assay using baby rabbit complement (rSBA) in a subset of 50 subjects per group (Groups 1 and 2)

Safety

To describe the safety profile of a booster dose of MenACYW conjugate vaccine, when given alone or when given concomitantly with a MenB vaccine.

The endpoints for the observational objectives are presented in [Section 9.3.1.1](#).

3 Investigators and Trial Organization

This study will be conducted in up to 40 centers in the US and Puerto Rico. The Principal Investigators and any sub-Investigators at the individual sites will be coordinated by 1 Coordinating Investigator. Details of the trial centers, the Investigators at each center, and the Coordinating Investigator are provided in the “List of Investigators and Centers Involved in the Trial” document.

An internal safety management team (SMT) will perform a blinded safety analysis on safety data after vaccination.

The Sponsor's Responsible Medical Officer (RMO) (the person authorized to sign this protocol and any amendments on behalf of the Sponsor) is [REDACTED]
[REDACTED].

4 Independent Ethics Committee / Institutional Review Board

Before the investigational product can be shipped to the investigational site and before the inclusion of the first subject, this protocol, the informed consent form (ICF) and the assent form, subject recruitment procedures, and any other written information to be provided to subjects must be approved by, and / or receive favorable opinion from, the appropriate Independent Ethics Committee (IEC) or Institutional Review Board (IRB).

In accordance with Good Clinical Practice (GCP) and local regulations, each Investigator and / or the Sponsor are responsible for obtaining this approval and / or favorable opinion before the start of the study. If the protocol is subsequently amended, approval must be re-obtained for each substantial amendment. Copies of these approvals, along with information on the type, version number, and date of document, and the date of approval, must be forwarded by the Investigator to the Sponsor together with the composition of the IEC / IRB (the names and qualifications of the members attending and voting at the meetings).

The Investigator will submit written summaries of the status of the study to the IEC / IRB annually, or more frequently if requested. All serious adverse events (SAEs) occurring during the study that are related to the product administered will be reported by the Investigator to the IEC / IRB, according to the IEC / IRB policy.

5 Investigational Plan

5.1 Description of the Overall Study Design and Plan

5.1.1 Study Design

The MET59 study is a Phase IIIb, open-label (the laboratory technicians will be blinded to group assignment), partially randomized, parallel-group, active-controlled, multi-center study to evaluate the antibody persistence 3-6 years after the priming vaccination with either MenACYW conjugate vaccine or the licensed Mencevo vaccine, and to evaluate the immunogenicity and safety of a booster dose of MenACYW conjugate vaccine when administered alone or concomitantly with licensed meningococcal serogroup B (MenB) vaccines in adolescents and adults in the US and Puerto Rico.

A total of 600 subjects who were vaccinated 3-6 years earlier in study MET50 are planned to be enrolled. Approximately 400 healthy adolescents and adults who had received 1 dose of either MenACYW conjugate vaccine (Group 1, N=200) or Mencevo vaccine (Group 2, N=200) as part of

the MET50 study will receive a booster vaccination with MenACYW conjugate vaccine. Approximately 200 healthy adolescents and adults who had received 1 dose of MenACYW conjugate vaccine will receive a booster vaccination with MenACYW conjugate vaccine administered concomitantly with a MenB vaccine (Group 3, MenACYW conjugate vaccine + Trumenba vaccine, N=100; and Group 4, MenACYW conjugate vaccine + Bexsero vaccine, N=100). If needed to meet enrollment requirements, MenACYW conjugate vaccine-primed subjects from the MET43 study could also be considered as source of subjects to be enrolled in Group 1, 3 or 4. Additionally, the population of Menveo vaccine-primed subjects could be enriched with individuals who received 1 dose of Menveo vaccine 3-6 years prior to enrollment in this trial as part of their regular adolescent vaccination schedule and who are 13-25 years of age; ie, non-MET50 subjects).

MenACYW conjugate vaccine-primed subjects (from either MET50 or MET43) will be randomized in a 2:1:1 ratio to receive 1 dose of MenACYW conjugate vaccine alone (Group 1) or to receive 1 dose of MenACYW conjugate vaccine concomitantly with 1 dose of a licensed MenB vaccine (Trumenba vaccine [Group 3] or Bexsero vaccine [Group 4]).

Subjects primed with Menveo vaccine in MET50 or outside of Sanofi Pasteur trials will be assigned to Group 2 (these subjects will not be randomized).

5.1.2 Justification of the Study Design

This study is part of the ongoing development program that focuses on demonstrating that MenACYW conjugate vaccine can provide broad coverage against circulating meningococcal strains from serogroups A, C, Y, and W in infants through older adults. MET59 is a study that will be conducted as part of the Phase IIIb development of MenACYW conjugate vaccine in which the vaccine candidate will be evaluated as a booster dose in adolescents/young adults. This study will describe the immunogenicity and safety of a booster dose of MenACYW conjugate vaccine given 3-6 years after a primary dose of MenACYW conjugate vaccine or Menveo vaccine was administered. This study will also describe the antibody persistence 3-6 years after primary vaccination prior to administration of the booster dose. Subjects who were included in study MET50 and MET43 are eligible to be enrolled in MET59.

5.1.3 Study Plan

Eligible subjects will be identified and recruited. Subjects who are ≥ 13 to < 18 years of age will sign an assent form and their parent / guardian will sign and date the ICF before any procedure or treatment associated with the trial is performed. Subjects who are 18 years of age and older will sign and date the ICF before any procedure or treatment associated with the trial is performed.

Vaccination

MenACYW conjugate vaccine-primed subjects (from either MET50 or MET43) will be randomized in a 2:1:1 ratio to receive 1 dose of MenACYW conjugate vaccine alone (Group 1) or to receive 1 dose of MenACYW conjugate vaccine concomitantly with 1 dose of a licensed MenB vaccine (Trumenba vaccine [Group 3] or Bexsero vaccine [Group 4]). Subjects primed with Menveo vaccine in MET50 or outside of Sanofi Pasteur trials will be assigned to Group 2 (these

subjects will not be randomized). Study vaccines will be administered according to the following schedule:

Group 1:	MenACYW conjugate vaccine on D0	(n=200)
Group 2:	MenACYW conjugate vaccine on D0	(n=200)
Group 3:	MenACYW conjugate vaccine + Trumenba vaccine on D0	(n=100)
Group 4:	MenACYW conjugate vaccine + Bexsero vaccine on D0	(n=100)

Note: In order to comply with the US Food and Drug Administration (FDA)-approved schedules for the respective MenB vaccines, subjects in Group 3 and Group 4 may choose to receive the second dose of MenB vaccine at Visit 2 (D30) after all the study procedures have been completed. Subjects in Group 3 should receive a third dose (or second dose if the alternate 2-dose Trumenba vaccine schedule is used instead by the study Investigators) of Trumenba vaccine on D180, which is not a study visit. These vaccinations for completion of the MenB schedules will take place outside of the objectives and scope of this study and thus will not be described in this protocol.

Blood sampling

All subjects will provide a pre-vaccination (baseline) blood sample on D0 and a post-vaccination sample on D30 (+14 days) (For subjects in Group 3 and Group 4, the post-vaccination blood sample will be provided prior to receiving a second dose of MenB vaccine on D30). A subset of the first 50 subjects enrolled in Groups 1 and 2 (total of 100 subjects) will provide an additional post-vaccination sample on D06 (± 1 day). This subset will have 3 visits in total.

Collection of safety data

Safety data will be collected as follows:

- All subjects will be followed for safety from Visit 1 to D180 after the last vaccination.
- All subjects will be observed for 30 minutes after vaccination on D0 and any unsolicited systemic AEs occurring during that time will be recorded as immediate unsolicited systemic AEs in the case report book (CRB)
- The subject or subjects' parent / guardian will record information in a diary card about solicited reactions from D0 to D07 after vaccination on D0 and unsolicited AEs from D0 to D30.
- SAEs (including AESIs) and MAAEs will be recorded throughout the study. The subject or subject's parent / guardian will record information in a diary card about possible SAEs and MAAEs from D0 to D30. Information about possible SAEs and MAAEs will also be recorded in a memory aid from D30 until the 6-month (+14 days) follow-up phone call. The subjects or subject's parent / guardian will be asked to notify the site immediately about any potential SAE at any time during the study.
- The completed diary cards will each be collected and reviewed with the subject's parent/ guardian at the subsequent visit.
- Staff will contact the subjects' parent/ guardian by telephone within 14 days after the vaccination visit (D0) to remind them about the forthcoming study visit. If the subject's

participation in the study is discontinued, the information recorded on the diary card will be reviewed at this time and the diary card will be retrieved by the site.

- Staff will contact the subject or subject's parent / guardian by telephone 8 days (+2 days) after the vaccination visit (D0) to identify the occurrence of any SAEs (including AESIs) and/or MAAEs not yet reported and to remind them to complete the diary card and to bring it back to the next visit.
- Staff will contact the subject or subject's parent / guardian by telephone at 6 months (+14 days) after vaccination on D0 to review the memory aid and identify the occurrence of any MAAEs and SAEs (including AESIs) that have not been reported.

5.1.4 Visit Procedures

Medical procedures (examinations, injections, etc.) must be conducted by appropriately licensed or credentialed study site staff working within the scope of their license / credentials.

D0 Visit: Inclusion, Randomization, Blood Sample, and Vaccination

1. **Subjects aged 13 to < 18 years^a:** Give the subject and the subject's parent / guardian information about the trial, answer any questions, obtain signed assent from subjects and the written informed consent (signed as below) from the subject's parent / guardian, and give him / her a signed copy of each.
Subjects aged 18 years^a and older: Give the subject information about the trial, answer any questions, obtain signed informed consent form from subject, and give him / her a signed copy.
2. Check inclusion and exclusion criteria for eligibility
3. Collect demographic data
4. Urine pregnancy test (if applicable)
5. Obtain verbal medical history about the subject
6. Conduct a history-directed physical examination, including temperature (a physical examination conducted during the same day as part of routine clinical care may be used for this purpose)
7. Contact the interactive response technology (IRT) system for randomization (except for subjects primed with Menveo vaccine which are allocated automatically to Group 2), allocation of subject number, vaccine group assignment, and blood sample subset assignment
8. Obtain the blood sample (see [Section 7.1](#) for detailed instructions regarding the handling of blood samples). If attempts to obtain the first blood draw are unsuccessful (3 attempts), then Visit 1 can be rescheduled to a later date at which point informed consent and

^a Or legal age of majority, if different from 18 years of age

inclusion/exclusion criteria must be re-validated. If the first blood draw cannot be obtained, the subject will be withdrawn from the study without being vaccinated.

9. Administer the MenACYW conjugate vaccine in the deltoid muscle. For subjects in Group 3 and Group 4, administer the concomitant vaccine in the opposite arm.
10. Keep the subject under observation for 30 minutes and record any AE in the source document.
11. Give the subject or subject's parent / guardian a diary card, a thermometer, and a ruler, and go over the instructions for their use.
12. Remind the subject or subject's parent / guardian to expect a telephone call 8 days after the D0 visit and to bring back the diary card when they return for the D30 (+14 days) visit at a specified date and time.
13. Remind the subject or subject's parent / guardian to notify the site in case of an SAE.
14. Complete the relevant (electronic) case report form CRF pages for this visit.

D06 Visit (D06 [+1 day] after D0 visit (100-subject subset only): Blood sample

1. Review temporary contraindications for subsequent blood sampling.
2. Obtain the blood sample (see [Section 7.1](#) for detailed instructions regarding the handling of blood samples).

Telephone Call 1 (D08 [+2 days] after D0 visit)

Note: If D08 falls on a weekend or a holiday, the telephone call may be made on the following business day.

1. Record relevant information concerning the subject's health status on the telephone contact form. If an SAE occurred, follow the instructions in [Section 10](#) for reporting it.
2. Remind the subject or subject's parent / guardian to do the following:
 - Complete the D0 to D07 pages of the diary card.
 - Complete the remaining pages of the diary card and bring them to D30 (+14 days) visit.
 - Notify the site in case of an SAE.

D30 Visit (+14 days after D0): Collection of Safety Information and Blood Sample

1. If the diary card information from D0 to D07 has not yet been obtained, obtain it at this time. Review the pages of the diary card with the subject or the subject's parent / guardian, including any AEs, medications, or therapy that occurred since vaccination
2. Review temporary contraindications for subsequent blood sampling (see [Section 5.2.7](#))
3. Obtain the blood sample (see [Section 7.1](#) for detailed instructions regarding the handling of blood samples) before administration of a second MenB vaccination (applicable to Groups 3 and 4 only, and given outside of the objectives of the study)
4. Give the subject or the subject's parent / guardian an MA
5. Complete the relevant (electronic) case report form CRF pages for this visit (including the trial termination record).
6. If the subject or the subject's parent / guardian does not return for the D30 visit, and the diary card is not received at the site, site personnel will contact the subject or the subject's parent / guardian by telephone. During the telephone call, the subject or the subject's parent / guardian will be reminded to return the diary card to the study site. Telephone calls will be documented on the Telephone / Interview Record. If the study personnel are unable to contact the subject or the subject's parent / guardian with 3 attempts, the study personnel will follow instructions given in [Section 5.2.9](#).

Safety Follow-up Telephone Call (D180 [+14 days] after D0 vaccination): Collection of SAEs and MAAEs

Review the MA and ask the subject or the subject's parent / guardian if the subject has experienced any SAEs since vaccination or any MAAEs since D30 (+14 days) visit.

- If an SAE has occurred, follow the instructions in [Section 10](#) for reporting it.
- If an MAAE has occurred, follow the instructions in the Operating Guidelines.

Follow-up of subjects with Related AEs or with AEs That Led to Study/Vaccination Discontinuation:

Unless a subject or subject's parent/guardian refuses further contact, each subject who experiences an AE (whether serious or non-serious) during the study must be followed until the condition resolves, becomes stable, or becomes chronic (even after the end of the subject's participation in the study) if *either* of the following is true:

- The AE is considered by the Investigator to be related to the product administered.
- The AE caused the discontinuation of the subject from the study or from vaccination.

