5.2.8 Conditions for Withdrawal

Subjects and/or the subjects' parents / guardians will be informed that they have the right to withdraw themselves or their child from the study at any time.

A subject may be withdrawn from the study:

- At the discretion of the Investigator or Sponsor due to safety concerns (withdrawal) without the subject's permission
- At the request of the subject (dropout)

The following will result in automatic withdrawal or exclusion of a subject from the study:

- Significant non-compliance with the protocol, on the basis of the Investigator's judgment

The reason for a withdrawal or dropout should be clearly documented in the source documents and in the CRB.

The Investigator must determine whether voluntary withdrawal is due to safety concerns (in which case, the reason for discontinuation will be noted as "Adverse Event") or for another reason.

Withdrawn subjects will not be replaced.

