6.4 Blinding and Code-breaking Procedures

MET59 is an open-label study; therefore, there is no need for code-breaking procedures.

Until database lock and to prevent biases, the laboratory personnel performing the serology testing will be blinded to the group assignment. The laboratory will have a written procedure detailing how the blinding will be maintained.

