6.5 Randomization and Allocation Procedures

MenACYW conjugate vaccine-primed subjects (from either MET50 or MET43) will be randomized in a 2:1:1 ratio to receive a booster dose of MenACYW conjugate vaccine alone (Group 1, 200 subjects) or to receive a booster dose of MenACYW conjugate vaccine concomitantly with licensed MenB vaccines (Trumenba vaccine; Group 3, 100 subjects, or Bexsero vaccine; Group 4, 100 subjects). Subjects primed with Menveo vaccine in MET50 or outside of Sanofi Pasteur trials will be assigned to Group 2 (200 subjects, which will not be randomized).

All subjects primed with MenACYW conjugate vaccine who meet the inclusion / exclusion criteria will be randomly assigned to Group 1, 3, or 4 in a 2:1:1 ratio, while subjects primed with Menveo vaccine will be automatically allocated to Group 2 (not randomized).

Site staff will call the IRT, enter identification and security information, and confirm a minimal amount of data in response to IRT prompts. The IRT will then state the vaccine dose assignment and whether the subject has been assigned to the D06 blood-draw subset. The full detailed procedures for randomization are described in the Operating Guidelines. If the subject is not eligible to participate in the trial, then the information will only be recorded on the subject recruitment log.

Subject numbers that are assigned by the IRT will consist of a 12-digit string (a 3-digit country identifier, a 4-digit study center identifier, and a 5-digit subject identifier). For example,

Subject 840000100005 is the fifth subject enrolled in Center Number 1 in the US (840 being the US country code).

Subject numbers should not be reassigned for any reason. The Research and Development (R&D) Site Quality Operations Department at Sanofi Pasteur will hold the randomization codes in a secured location.

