7.1 Sample Collection

At the D0, D06 and D30 visits, 20 mL of blood will be collected in tubes provided by or recommended by the Sponsor. Immediately prior to the blood draw, the staff member performing the procedure will verify the subject’s identity as well as the assigned subject’s number and sampling stage on the pre-printed label, and will attach the label to the tube. When vaccination and blood sample collection occur at the same visit and vaccine is given only in one of the arms, blood is to be taken from the limb opposite to the one that will be used for vaccination, if possible.

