12.2.1 Full Analysis Set

The FAS is defined as the subset of subjects who received at least 1 dose of the study vaccine and had a valid post-vaccination serology result. Two FAS will be defined (FAS1 for D06 and FAS2 for D30). All subjects will be analyzed according to the treatment group to which they were randomized or assigned.

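### The D0 visit randomises and releases the open-label group before the mandatory baseline blood draw, leaving a small, avoidable route to selection after allocation in the Group 1 versus Groups 3 and 4 comparison

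*Protocol*

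**What the plan says.** Protocol 5.1.4 sets out the D0 visit as a numbered sequence, and the visit's title gives the same order.

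- **Step 7, allocation.** "Contact the interactive response technology (IRT) system for randomization (except for subjects primed with Menveo vaccine which are allocated automatically to Group 2"). The same contact gives the subject number, the vaccine group and the blood-sample subset.
- **Step 8, baseline draw.** "If attempts to obtain the first blood draw are unsuccessful (3 attempts), then Visit 1 can be rescheduled to a later date"; consent and the inclusion and exclusion criteria are then checked again. If no sample is ever obtained, "If the first blood draw cannot be obtained, the subject will be withdrawn from the study without being vaccinated".
- **Step 9, vaccination.**

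The arm is not concealed between steps 7 and 8. Protocol 6.4 says "MET59 is an open-label study; therefore, there is no need for code-breaking procedures" and blinds only the serology laboratory. Protocol 6.5 says "The IRT will then state the vaccine dose assignment and whether the subject has been assigned to the D06 blood-draw subset" and leaves the detailed randomisation procedure to the Operating Guidelines.

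On losses, Protocol 5.2.8 allows withdrawal at any time and says "Withdrawn subjects will not be replaced". The FAS (Protocol 12.2.1) takes subjects who "received at least 1 dose of the study vaccine and had a valid post-vaccination serology result". The PPAS is a subset of the FAS, and the SafAS also needs a dose. FAS3, added in SAP 5.2.1.2, needs a valid pre-vaccination serology result.

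**The concern.** Group 1 against Groups 3 and 4 is the only comparison in the trial protected by randomisation; Group 2 is assigned by priming history. It serves Secondary Objective 5 and the description of safety with and without a MenB vaccine.

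Where a step that can end participation follows release of the arm in an open-label trial, decisions at that step can depend on the arm. Three are exposed here: how hard the site tries for a difficult sample, whether the subject returns for a rescheduled visit, and how the criteria are judged the second time. Exclusions 17 and 18 rest on investigator judgment, and exclusion 19 (recent antibiotics) can newly arise between visits.

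The arms differ visibly. Groups 3 and 4 receive a second injection and a MenB vaccine, while the first subjects in Group 1 have an extra visit and draw at D06. If losses depended on arm, the vaccinated groups would no longer be exactly the randomised ones, and no immunogenicity or safety set would restore subjects lost through a failed draw.

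**Working it through.** **1. Where a randomised but unvaccinated subject is counted**

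| Set | Requirement | Draw failed | Bled, then declined vaccine |
|---|---|---|---|
| FAS1, FAS2 | dose and post-vaccination result | out | out |
| PPAS1, PPAS2 | subset of FAS | out | out |
| SafAS | dose and safety data | out | out |
| FAS3 (SAP) | valid D0 result | out | can be in |

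**2. Possible number lost.** No rate is documented. With an assumed 1-3% for failed draw, failed re-validation or refusal together, applied to 200 + 100 + 100 = 400 randomised: 400 × 0.01 = 4 and 400 × 0.03 = 12. If spread evenly, that is 2-6 in Group 1 and 1-3 in each of Groups 3 and 4.

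**3. Power.** First, the plan's own figure (Protocol 12.5.2):

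- At n = 89, the one-sided 97.5% Clopper-Pearson lower limit exceeds 75% from 75 responders upward (exact one-sided error 0.0248).
- Serogroup A power is 0.9964 in Group 1 (rate 0.922) and 0.9590 in Group 2 (rate 0.896). C, Y and W exceed 0.99 in both groups and round to 1.
- Joint power: 0.9964 × 0.9590 = 0.9555, which agrees with the stated 96%.

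The planned drop-out gives 600 × 0.85 = 510, hence 200 × 0.85 = 170 in each of Groups 1 and 2 and 100 × 0.85 = 85 in each of Groups 3 and 4. Next, an assumed extra pre-vaccination loss f is taken on top of the 15%, so n = N × (1 − f) × 0.85, rounded down:

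| Extra loss f | Groups 1 and 2, each | Power, weakest endpoint (Group 2, A) | Groups 3 and 4, each |
|---|---|---|---|
| 0% | 170 | 99.93% | 85 |
| 2% | 166 | 99.90% | 83 |
| 5% | 161 | 99.88% | 80 |
| 10% | 153 | 99.78% | 76 |

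Group 1 or Group 2 could lose 200 − 89 = 111 subjects (55.5%) before reaching 89.

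**4. Largest possible shift in the randomised comparison.** Take a true seroresponse p = 0.922 and let an arm lose a fraction f.

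- If all those lost were non-responders, the observed rate rises by p·f/(1 − f). At f = 0.03: 0.922 × 0.03 / 0.97 = 0.0285.
- If all were responders, it falls by (1 − p)·f/(1 − f). At f = 0.03: 0.078 × 0.03 / 0.97 = 0.0024.
- With the two arms pushed in opposite directions: 2.85 + 0.24 = 3.1 percentage points.

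For scale, the approximate 95% half-width for 170 against 85 subjects at p = 0.922 is 1.96 × √(0.922 × 0.078 × (1/170 + 1/85)) = 1.96 × 0.0356 = 0.070, or 7.0 points. The 3.1-point bound assumes up to 3% lost in each arm; losses concentrated in one arm would raise it.

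**The case against.** The strongest reply is that the reordering misses the most plausible arm-dependent mechanism. Failed venepuncture has little reason to depend on arm, whereas reconsidering after hearing the arm does, and that stays possible in any open-label trial where the group is released before vaccination. This stands. Drawing first moves failed draws and failed re-validations ahead of allocation and shortens the window for refusal, but does not close it.

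Four stronger readings are tempting, and the documents do not support them.

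- **The losses vanish from every analysis.** A subject bled at D0 who then declines vaccine meets the FAS3 definition. The SAP also plans baseline demographics on everyone randomised or assigned (5.1.4) and refers to a disposition table (4.4.2.5.6), so losses can be counted by arm.
- **The primary objectives are at risk.** They are single-group tests against 75%, with numbers well above 89, and the 15% drop-out already runs from enrolment.
- **The randomised comparison is invalidated.** It is descriptive, and its immunogenicity part is run on the PPAS, which already excludes subjects for several post-randomisation reasons. Nothing in the documents links dislike of a second injection to hSBA response.
- **The subject is told the arm at step 7.** The text says only that the IRT states it to site staff. Whether the allocation stands at a rescheduled Visit 1 is not stated either, and the Operating Guidelines may cover both points.

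On timing, the planned inclusion period ended on 02 March 2020 and the protocol history dates version 6.0 to 06 April 2020. By that calendar few or no D0 visits may remain. This limits the practical value of reordering but does not mend the written sequence.

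**Conclusion.** The point holds as an avoidable weakness of small size. The written order releases an open-label allocation before a step that decides whether the subject is vaccinated. It also lets that step be repeated, possibly days later, with partly judgment-based criteria reapplied by staff who know the arm.

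The effect is confined to the randomised comparison of Group 1 with Groups 3 and 4. At an assumed 1-3% it concerns 4-12 of 400 subjects and, at up to 3% lost in each arm, cannot move a seroresponse difference by more than about 3 points, against a half-width of about 7 points. There is no material effect on power or on the primary tests.

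Three assumptions carry this: the loss rate, which the documents do not give; a seroresponse of 0.922 in both arms for the bound; and the inference, from the open-label design and the IRT text, that the arm is known to staff during the draw. Actual dependence of losses on arm is a possibility, not something the documents show.

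**What to change.** In Protocol 5.1.4 and both Tables of Study Procedures, split the IRT contact in two:

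1. The IRT issues the subject number only. This suffices for the tube, since Protocol 7.1 has staff check the subject's number and the "sampling stage on the pre-printed label".
2. The site reviews blood-sampling contraindications, draws the D0 sample and confirms in the IRT that it was obtained.
3. The IRT then randomises, or allocates to Group 2, and releases the vaccine group and D06 subset. Vaccination follows immediately.

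The rescheduling rule then operates entirely before allocation. The Protocol 7.1 preference for bleeding the limb opposite a single injection can still be met by choosing the injection arm after the draw. SAP Tables 3.1 and 3.2 should be aligned.

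The cost is protocol wording, an IRT setting and one more IRT step in the same visit. No procedure, visit or subject is added.

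In either case, add to the SAP a table of everyone randomised or assigned but not vaccinated, by assigned group and reason, separating failed draw, failed re-validation and refusal. The reasons in Protocol 5.2.10 do not make that split: refusal of blood sampling and refusal of vaccination share one category, and a failed draw has none of its own. If enrolment has closed, this table is the usable remedy.
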